Aim #2 (R61): To confirm the functional relationship of auditory plasticity improvements. In prior studies, auditory plasticity deficits have been related to impairments in higher, functionally relevant auditory functions. *Hypothesis: We hypothesize that plasticity outcomes will be related to functionally relevant outcomes (auditory cognition³, primary), emotion recognition (AER)¹⁰, MMN, θ -ITC, other functional outcomes and pharmacodynamics.*

Aim #3 (R33): To evaluate effects of D-serine-enhanced auditory plasticity on auditory cognition. 60 Sz patients will be randomized to auditory remediation + D-serine or placebo. 16 sessions (1x week) of treatment will be utilized, with dose dependent on R61 results. *Hypothesis: We hypothesize that D-serine treated subjects will have greater improvements in auditory cognition³ than placebo. Plasticity, AER, MMN, θ -ITC, reading, other cognitive/functional measures and pharmacodynamics will be secondary outcomes.*

Inclusion/Exclusion Criteria

This section details your study sample(s) and addresses the requirement for risk minimization.

You may choose to divide your sample by population (healthy controls vs. subjects) or by procedure (subjects who will have an MRI) and then define different sets of criteria for each.

For each sample, create or insert a table to describe detailed criteria for study inclusion and exclusion and the method you will use to ascertain each criterion. The method of ascertainment may describe tests, scales and instruments. When relevant, indicate the level of training of the person who will make the assessment (e.g. clinical interview by a psychiatrist).

Inclusion/Exclusion Criteria needs to be numbered and listed in outline form (see Table template below).

CRITERION	METHOD OF ASCERTAINMENT
Inclusion:	
1. Age between 18-50	Self-report
2. DSM-V diagnosis of schizophrenia or schizoaffective disorder	SCID
3. Auditory Cognitive impairment demonstrated by: 1. MATRICS composite score (MCCB) composite domain score less than or equal to 0.5 standard deviation below normal (T score less than or equal to 45) 2. And at least one of the following: a. MCCB verbal memory domain score less than or equal to 0.5 standard deviation below	Screening MCCB

normal (T score less than or equal to 45) b. Tone matching score of less than or equal to 77.7%	
4. Willing to provide informed consent	Physician evaluation

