Provide a clear, concise narrative of study procedures with special attention to the subjects' involvement. Detail the overall study timeline and location of study procedures, list all interventions, assessments and interviews, estimate the duration of each procedure, provide dosing schedules, identify study personnel involved in each procedure, and provide credentials for relevant personnel. For complicated study designs, we strongly encourage attaching tables, flow-charts, and study algorithms.

In the R61, we will confirm target engagement of D-serine + auditory remediation, assess relationships of plasticity changes and cognition, safety and assess the optimal dose of D-serine treatment. In the R33, we conduct a randomized, placebo-controlled, parallel group study with the superior dose of D-serine combined with 16 weekly sessions of the same neuroplasticity-based auditory remediation. The structure of this grant requires successful completion of the R61 phase over 2 years prior to initiation of the R33 phase. We will amend the PSF and consent to include a full description of the R33 phase prior to its initiation.

The study will be conducted in groups of 15 subjects in which 12 subjects will receive D-serine for each of the three treatment visits and 3 will receive placebo for each of the three treatment visits. The first group of 15, will receive 80 mg/kg or placebo, and the second group of 15 subjects will receive 100 mg/kg or placebo, followed by a third group receiving 120 mg/kg or placebo. As previous studies noted minimal carry over effect of D-serine effects ([name] 2010), subjects may be permitted to participate in more than one phase with at least a six

month space in between.

If there are tolerability concerns at the 80 or 100 mg/kg doses, we will add a 60 mg/kg arm, ensuring the assessment of multiple doses. After each cohort, we will obtain permission from both the FDA and the IRB via an amendment, prior to the beginning of the next cohort. We require this safety milestone to be reached in order to begin the next cohort.

R61 Design (Table 1):

R61 Design	Table 1 (R61)	Baseline	Treatment Day			Follow-up ¹
			1	2	3	
		Day -30 to -1	Day 1	Day 8±2	Day 15±2	
	Consent	x				
	Medical screening	x				
	D-serine/Placebo		x	x	x	
	MMN		x	x	x	
	Auditory Remediation/EEG		x	x	x	
	Cognitive and behavioral ratings	x				
	Clinical laboratory/pregnancy/vitals	x	x	x	x	x
	SAFTEE/C-SSRS	x	x	x	x	x
	1. If necessary to follow-up any abnormalities.					

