Screening/Informed consent: Informed consent will be obtained before any study procedures, including screening procedures, are initiated. After providing informed consent, subjects will undergo full medical screening (medical history, physical examination, vital signs, laboratories for basic chemistries, blood counts, liver function tests, urinalysis, urine toxicology, serum pregnancy test for women, and thyroid tests, electrocardiogram [EKG]) and psychiatric screening (i.e., Structured Clinical Interview for DSM V Axis I Disorders (SCID) to confirm eligibility. Screening will occur over an up to 31-day screening period.

Baseline ratings: Eligible subjects will then undergo baseline cognitive and behavioral tests:

Randomization: Assignment to treatment groups will be on a random basis. Randomization will be stratified by baseline tone matching.

Auditory remediation visits: Subjects will then undergo three auditory remediation/EEG sessions. Each visit will follow the same format. Sessions are administered once a week±2 days. We utilize an auditory remediation program, in which participants are presented with paired tones (e.g. Stimulus 1 (“reference”) and Stimulus 2 (“test”): S1 and S2) and indicate which tone is higher in pitch (frequency). In the first pair, the ratio is 50% (e.g. 1000±500 Hz), and the difficulty level is adjusted to maintain a steady (~70% correct) level of performance across the 80 repeats. Ratios in each pair are log-transformed and averaged across 10-trial pairs (e.g., pairs 1-10, 11-20, etc.). When the reference (S1) remains constant (“fixed”), highly significant improvement is seen.

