## **Statistical Analysis Plan & Power**

Before any specific statistical techniques are applied, we will examine all variables at all time points for illegitimate values, outliers, and other inconsistencies. Distributions of demographic variables and other clinically important baseline variables will be examined and summarized by means, standard deviations, minima, and maxima for continuous measures and proportions for categorical measures. We will make every effort to obtain all data to reduce or eliminate missing data issues. Intent-to-treat analysis will be implemented for all estimation and testing. Tests will be two-sided and statistical significance determined by  $p < 0.05$ .

**R61 Component.** Summaries of clinical and demographic variables will be provided for each of the three cohorts (C1) D-serine 80mg/kg (n = 12) vs. placebo (n = 3), (C2) D-serine 100mg/kg (n = 12) vs. placebo (n = 3), and (C3) D-serine 120mg/kg (n = 12) vs. placebo (n = 3). As a precaution, any indication of imbalance on important baseline measures between treatment arms (despite randomization) will trigger investigation of whether differences in the primary outcome measures are attributable to these imbalances. For analyses described below, the placebo groups from each of the three cohorts will be combined to yield an effective placebo group of n = 9, unless descriptive analyses suggest systematic differences between the three placebo groups, in which case the groups will remain separate in subsequent analyses.

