Aim 1 Analysis: Aim 1 hypothesizes that D-serine will lead to greater plasticity, MMN, and theta-ITC changes than placebo, with the largest effect being seen at the 120mg/kg dose. Plasticity improvement (defined as change from trials 20 – 30 to trials 70 – 80 at end of session) in the 3rd week of treatment will be examined by using Cohen's d effect size estimates. Within each D-serine group, Cohen's d for within-subject change will be computed by taking the mean change in plasticity divided by the pre-treatment standard deviation. Similar Cohen's d values will be computed for the combined placebo group. Corresponding 95% confidence intervals (based on standard theory or constructed via bootstrapping if assumptions for constructing the confidence intervals based on parametric methods are not satisfied) will be computed. Similar procedures will be followed for assessing within-subject changes in MMN and theta-ITC. For each D-serine dose level, Cohen's d for between-group differences will be computed as (mean change for the D-serine group minus mean change for the placebo group) divided by standard deviation of the change scores in the combined placebo group.

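### The between-group plasticity effect size stated for Aim 1 leaves out baseline tone matching, the factor by which randomisation is stratified

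*Protocol*

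**What the plan says.** Protocol, Study Procedures (Randomization): "Randomization will be stratified by baseline tone matching". The number of strata and the cut-points are not given.

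Protocol, Study Procedures, on the cohorts: in each group of 15, "12 subjects will receive D-serine for each of the three treatment visits and 3 will receive placebo". The cohorts run one after another at rising dose.

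SAP, R61 Component: unless descriptive analyses suggest systematic differences between them, "the placebo groups from each of the three cohorts will be combined to yield an effective placebo group of n = 9". On baseline, "any indication of imbalance on important baseline measures between treatment arms (despite randomization) will trigger investigation". That step names neither tone matching nor a method.

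SAP, Aim 1 Analysis: at each dose the between-group d has as its numerator "mean change for the D-serine group minus mean change for the placebo group". To give d, this raw contrast is then "divided by standard deviation of the change scores in the combined placebo group". The formula has no stratum term and no covariate. Confidence intervals are described for the within-group effect sizes. The supplied text ends at the between-group formula and states no interval for it.

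**The concern.** A factor used to stratify randomisation is normally carried into the analysis. It was thought important enough to balance, and if it predicts outcome, adjusting for it sharpens the estimate and removes the effect of whatever imbalance is left. The stated formula does not do this.

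Two features of this design make the omission matter more than usual. Three placebo patients per cohort allow only coarse stratification; with two strata they must split 2 and 1. Each dose arm is then compared with nine placebo patients, six of whom were randomised in other cohorts, so balance within a cohort does not carry over to the contrast that is reported.

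Leaving the question of adjustment until imbalance has been seen also leaves a choice to the analyst in a comparison of 12 with 9. At stake are the precision of each dose's effect size and, if the patient mix changes over time, its accuracy.

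**Working it through.** **Inputs.** From the documents: 12 D-serine and 3 placebo per cohort, three cohorts, placebo pooled. Assumed, because the documents do not give them: r, the correlation of baseline tone matching with plasticity change (0 to 0.5 shown); the strata; and any drift between cohorts. Baseline and change are each scaled to SD 1.

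**1. Counts.** 3 × 3 = 9 pooled placebo patients, as the SAP states, and 3 × (12 + 3) = 45 in all. For any dose, 3 of the 9 are concurrent and 6 are not.

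**2. Precision of the stated contrast.** SE = √(1/12 + 1/9) = 0.441 SD.

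**3. Gain from adjustment.** Without stratification, the SE ratio (adjusted to unadjusted) is √[(1 − r²)(1 + 1/(f − 2))], where f is the within-arm degrees of freedom. For a four-arm model f = 45 − 4 = 41. The ratios are then √(1 + 1/39) = 1.01 at r = 0, √(0.91 × 1.0256) = 0.966 at 0.3 and √(0.75 × 1.0256) = 0.877 at 0.5. Stratification already secures part of this gain, so it was simulated: 20,000 trials per scheme, independent patients, true difference 0.5, no drift. The median-cut row also takes in a repeat of 6,000 trials.

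| Assumed strata | SE ratio, r = 0 | r = 0.3 | r = 0.5 | Imbalance > 0.5 SD |
|---|---|---|---|---|
| Median cut (several forms) | 1.01 | 0.97-0.98 | 0.90-0.92 | 13-19% |
| Cohort tertiles | 1.005 | 0.985 | 0.942 | 8% |
| 90/10 cut | 1.01 | 0.967 | 0.882 | 24% |
| None | 1.01 | 0.966 | 0.877 | 26% |

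The unstratified row agrees with the formula. Its last entry is P(|Z| > 0.5/0.441 = 1.13) = 0.26.

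**4. On the scale of the SAP's d** (placebo-SD denominator, median cuts). The sampling SD goes from 0.53 to about 0.52 at r = 0.3 and from 0.51 to 0.47 at r = 0.5. In a single trial the adjusted and unadjusted d differ on average by 0.04 at r = 0, 0.09-0.10 at 0.3 and 0.14-0.16 at 0.5.

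**5. What a chance imbalance does.** A baseline difference of 0.5 SD moves the unadjusted difference by r × 0.5, which is 0.15 SD at r = 0.3 and 0.25 SD at r = 0.5.

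**6. Drift between cohorts.** Let mean baseline be −δ, 0 and +δ in cohorts 1, 2 and 3. Pooled placebo then averages 0, while the third-cohort dose arm averages +δ, so the unadjusted contrast is biased by r × δ. At δ = 0.5 this is 0.15 SD (r = 0.3) and 0.25 SD (r = 0.5). A simulation with a two-stratum split gave 0.17 and 0.28; the extra 0.02-0.03 comes from the uneven 7/8 split of 15 patients that it assumed. The adjusted contrast was biased by about 0 in every case. The first cohort has the opposite bias and the second none.

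**The case against.** The strongest reply is that the SAP text supplied is incomplete. Its heading promises power and its opening paragraph speaks of tests, yet neither a power calculation nor a named test appears, so an adjusted model may be described elsewhere. This stands, and it confines the point to the formula that is stated.

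Next, the value of r may be small. Baseline tone matching appears to be a percentage score: inclusion criterion 3 uses "Tone matching score of less than or equal to 77.7" per cent. The outcome is a within-session change in log-ratios on a task where "the difficulty level is adjusted to maintain a steady (~70% correct) level of performance across the 80 repeats". Nothing in the documents shows that the first predicts the second. This also stands. At r of 0.3 or below the gain in SE is at most about 3%. In a two-group analysis of 12 against 9, power at an assumed d of 0.5 is 0.19 unadjusted, 0.19 adjusted at r = 0.3 and 0.23 at r = 0.5.

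Third, stratification and the imbalance check already deal with the matter. This stands only in part. Stratification reduces imbalance but does not secure balance against a placebo group pooled over cohorts. The check is conditional, names no method and comes after the data have been seen.

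Last, drift is an assumption. That is so, but it is a plausible risk when cohorts are sequential, and the SAP's descriptive comparison of placebo groups rests on three patients each.

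**Conclusion.** The point holds as a modest improvement to the stated formula, for plasticity only. Without drift between cohorts, leaving out the stratifier costs nothing at r = 0, about 2-3% in SE at r = 0.3 and about 8-10% at r = 0.5, under median-cut strata. Chance imbalance above 0.5 SD is left unadjusted in roughly 13-19% of trials. If baseline tone matching drifts between cohorts and predicts change, there is bias as well: about 0.15-0.28 SD for the third cohort at r = 0.3-0.5 and an assumed drift of 0.5 SD per cohort. All of this rests on assumed r, strata and drift.

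A reader might infer more, and the documents do not support it:

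- That the planned estimate is biased as it stands. Bias needs both drift and a prognostic baseline, and neither is documented.
- That the plan contains no adjusted analysis. The supplied SAP is partial.
- That the go/no-go decision is affected. The Protocol (Milestones and Rationale) leaves the full criteria to another document.
- That MMN and theta-ITC share the problem. Nothing here bears on how tone matching relates to them.

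**What to change.** In the SAP's Aim 1 Analysis, pre-specify for plasticity one linear model with arm (pooled placebo and three doses) and continuous baseline tone matching. The continuous score avoids depending on strata that are not defined.

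- Report each adjusted dose-versus-placebo difference with its 95% CI.
- Form d from the adjusted difference and the placebo SD of change that the SAP already uses. Dividing by the residual SD would inflate d by 1/√(1 − r²), turning 0.50 into 0.52 at r = 0.3 and 0.58 at r = 0.5.
- Show the unadjusted d alongside, and keep the existing imbalance check as a sensitivity analysis.
- If the SAP's rule keeps the placebo groups separate, fit the same model within each cohort.
- State that the model corrects for baseline differences in tone matching but not for other drift in the outcome. For example, an outcome drift of 0.25 SD per cohort would still leave the pooled third-cohort contrast off by about 0.25 SD.

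No new data are needed, since the score is already collected for stratification. The cost is one degree of freedom (41 to 40). If tone matching is not prognostic, intervals are about 1% wider in the four-arm model (1.79 against 1.77 SD). In a two-group 12 versus 9 analysis the SE rises by about 3%, √(1 + 1/17) = 1.03. Within a single cohort of 12 and 3 it rises by about 4%, √(1 + 1/11) = 1.04.

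Separately, the Protocol's Antipsychotics paragraph plans dose changes as covariates and the stated SAP formula has none; the two should be reconciled.

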Study overview: Schizophrenia (Sz) is a major public health problem that affects ~1% of the population worldwide. Sz is associated with deficits in neurocognition¹⁻⁴ that represent a core feature of the disorder and that may precede illness onset⁶, and predict impaired psychosocial function^{7,8}. When comprehensive neurocognitive batteries are used, patients show deficits across a large variety of cognitive domains, suggesting widespread cortical involvement. In addition, Sz patients show reduced neuroplasticity in tasks designed to produce learning, leading to reduced ability to benefit from various forms of cognitive remediation⁹⁻¹¹. The effects of intervention strategies aimed at remediating neuroplasticity deficits, however, have been evaluated to only a limited degree. *Thus, remediating neuroplasticity is a rate-limiting first step prior to remediating cognition and overall function. Plasticity represents an unmet clinical need and a clinically relevant target. The goal of this NIMH sponsored two-site, two-phase R61-R33 study is to enhance efficacy and efficiency of auditory cognitive remediation by augmenting with D-serine.*

For both the R61 and R33 phase, we utilize the same neuroplasticity-based auditory remediation program which has demonstrated a dynamic, direct link between behavioral/neurophysiological plasticity and cognitive improvements.

The R61 phase is designed to assess whether D-serine has dose dependent target engagement over 3 sessions (1x week) of auditory remediation.

During the R61, we will confirm target engagement, pharmacodynamics, functional relationships and the optimal dose (80 vs. 100 vs. 120 mg/kg, IND: 122821) of D-serine treatment combined with 3 sessions of our auditory remediation program. *As previously, D-serine will be given 30 minutes before sessions, allowing for auditory remediation during peak serum levels and a pharmacodynamic assessment.* Successful completion of the R61 (go/no go) is defined by \geq moderate effect size change in auditory plasticity, MMN and θ -ITC, plus a moderate effect size correlation with functionally relevant cognitive measures ("auditory cognition": without safety issues).

In the R33, we directly evaluate functional improvement as an outcome, assessing the sustained effects of D-serine + 16 sessions (1x week) of the same auditory remediation program used in the R61.

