After a negative urine pregnancy test for fecund women and the Columbia Suicide Severity Rating Scale (C-SSRS), each visit will begin with a pretreatment EEG/capping. Subjects will then receive D-serine or placebo. Auditory remediation will begin 30 minutes after study drug administration, to allow for training during peak D-serine levels ([name], Malhotra et al. 2010). EEG will be recorded during sessions, to assess theta-ITC and secondary EEG measures. Immediately after auditory remediation, subjects will complete post treatment MMN. A D-serine level will be drawn immediately after the session using established methods to allow for functional pharmacodynamics readout, along with urinalysis and clinical laboratory assessments. The SAFTEE will be used to assess general side effects. Columbia/NKI EEG labs are both under the supervision of Drs. [name] and [name] and have previously conducted parallel studies, ensuring cross-site validation.

Study drug and maintenance of the blind: D-Serine and placebo will be administered as a solution, prepared (premixed) in water and prescribed only as “study medication.” D-serine will be dosed by weight (e.g. 80 mg/kg

for the 1st cohort). Study medication will be dispensed to subjects in individual, identical appearing bottles, and dispensed on the day of the session by an un-blinded pharmacist otherwise uninvolved in the study. As previously, D-serine will be obtained from Evonik, and an artificial sweetener will be used as placebo.

The un-blinded pharmacist, based upon predetermined assignment schedule, will make study assignment. Envelopes containing treatment assignment will be kept in pharmacy and in patients' clinical charts. Envelopes will be unsealed only in cases of medical necessity. Blind-breaks will be on individual subject basis only. The pharmacist does not participate in assessing any dependent variable and conveys no information about drug status to patients or staff except in a medical emergency.

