Interviews and neuropsychological assessments are associated with minimal risk. Some participants may find the interviews and assessments tiring or distressing. Risks are to be minimized by allowing as much flexibility in the interview process (e.g., doing the interview in several meetings, giving breaks) as possible. If subjects have emotional responses, appropriate psychological support is given. Most patients find the interviews and assessments helpful.

Pregnant or Nursing Females

We will not administer experimental medication to pregnant females. For these reasons, pregnant females are excluded from the study. All female patients will demonstrate a negative urine human chorionic gonadotropin (HCG) test prior to sessions to confirm that the patient is not pregnant.

Emergencies

If, during the course of interviewing and assessment procedures, study staff identifies a condition that mandates immediate clinical intervention or official reporting (e.g., homicidality/suicidality), all necessary steps will be taken, and

the emergency procedures of the Division of Experimental Therapeutics, inpatient unit NKI, and the Lieber Clinic will be followed. In the case that staff determine that the participant is at significant risk for self or other destructive behavior, any mental health professional currently treating the participant will be contacted and necessary treatment steps will be taken (e.g., hospitalization, continuous observation, referral to a care provider, etc.). All patients will be given numbers to call in the event of an emergency during treatment: the primary phone number of the treating clinician and the number for the Lieber clinic (both the front desk number and the number for the Doctor- on-call beeper). If the treating clinician, a covering MD in the Lieber clinic, NKI, or the Doctor- on- Call is immediately unavailable, the subject will be instructed to not delay and to go to their nearest Emergency Room.

COVID-19 risks

Going out in public and traveling involves some risk of infection with COVID-19. There is risk of COVID-19 infection during in-office visits and during travel for research purposes.

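### Site is neither a named stratification factor nor a term in the dose-versus-placebo effect size, so a site mix that shifts between the sequential dose cohorts enters the estimated effect

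*Protocol*

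**What the plan says.** The protocol's Study overview describes the project with the words "The goal of this NIMH sponsored two-site, two-phase R61-R33 study". Under Auditory remediation visits, it says that the EEG laboratories at the two institutions share supervision and "have previously conducted parallel studies, ensuring cross-site validation".

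On the design, Study Procedures says "The study will be conducted in groups of 15 subjects", of whom 12 receive D-serine "and 3 will receive placebo for each of the three treatment visits". The 80, 100 and 120 mg/kg cohorts follow one another, so dose and cohort are the same factor. On allocation it says "Randomization will be stratified by baseline tone matching". The un-blinded pharmacist works from a schedule fixed in advance; the text does not say whether there is one list or one per site.

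The SAP (R61 Component) merges the three placebo groups into one of 9, "unless descriptive analyses suggest systematic differences between the three placebo groups". Under Aim 1 Analysis, the between-group d for each dose is the difference in mean change between that dose group and combined placebo, divided by the placebo SD of change. Site does not appear in that formula. The SAP also calls for a look at baseline imbalance between arms, without naming site.

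**The concern.** Within a cohort, randomisation makes the active and placebo subjects comparable in expectation, site included. The planned contrast is not within a cohort. It sets 12 subjects from one cohort against 9 placebo subjects, 6 of whom come from the other two cohorts. Randomisation does not protect that comparison against anything that changes between cohorts, and the share recruited at each site is an obvious candidate.

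If change in plasticity, MMN or theta-ITC differs by site, such a shift moves d for one dose up and for another down. This bears on two decisions. The protocol makes progress to R33 depend on at least a moderate effect size, and the R33 dose depends on the R61 results. The placebo-pooling check is exposed as well: between three groups of 3, a difference in site mix looks the same as a difference between cohorts. If the check trips, each dose is left with a comparator of 3 instead of 9.

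**Working it through.** **Inputs from the documents.** Two sites; three sequential cohorts of 15 (12 active, 3 placebo). The plan's own counts reproduce: 3 × 15 = 45 subjects and 3 × 3 = 9 pooled placebo.

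**Assumptions, not in the documents.** The site split, and a site difference in change scores of 0.5 SD (in placebo change-score SD units). A different site difference scales every shift in d below in proportion.

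**1. Stable site mix, site not used in allocation.** Let a of 15 subjects in each cohort come from site A, and let k be the number of placebo subjects from site A in a cohort. The site-A share is (a − k)/12 in the dose group and (k₁ + k₂ + k₃)/9 in pooled placebo.
- The difference has mean 0.
- Its variance is Var(k) × [(1/12 + 1/9)² + 2 × (1/9)²] = Var(k) × 0.0625.
- At 8:7, Var(k) = 3 × (8/15) × (7/15) × (12/14) = 0.64, so the SD is √(0.64 × 0.0625) = 0.20.
- In d, 0.20 × 0.5 = 0.10.
- In a simulation of 100,000 allocations, the 95th percentile of the absolute difference in share was 0.36, or 0.18 in d.

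**2. Site mix drifting 11:4, 8:7, 4:11.** The expected site-A share in pooled placebo is (11 + 8 + 4)/45 = 0.511.

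| Cohort | Expected share, dose group | Minus pooled placebo | Shift in d at 0.5 SD |
|---|---|---|---|
| 80 mg/kg | 11/15 = 0.733 | +0.222 | +0.11 |
| 100 mg/kg | 8/15 = 0.533 | +0.022 | +0.01 |
| 120 mg/kg | 4/15 = 0.267 | −0.244 | −0.12 |

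Unlike case 1, these are expected values and do not average out. Between the highest and lowest dose, the two d values move apart by 0.467 × 0.5 = 0.23. The signs reverse if the other site shows the larger change.

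**3. Would allocating placebo within site remove the drift?** No. With each site given 1 or 2 of the 3 places, the mean differences in share in case 2 are about +0.24, +0.02 and −0.26. At a stable 8:7 mix, within-site allocation does cut the SD in case 1 from 0.20 to 0.12.

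**4. Precision with a site term.** In SD units, and treating the denominator of d as known, the unadjusted dose-minus-placebo difference has standard error √(1/12 + 1/9) = √0.1944 = 0.441. A site term adds (difference in share)² / W to the variance, where W is the within-group sum of squares of the site indicator.
- With the expected shares of case 2, W ≈ 2.35 + 2.99 + 2.35 + 2.25 = 9.93.
- For the largest gap, 0.244²/9.93 = 0.0060. The standard error becomes √0.2005 = 0.448, an increase of about 1.5%.
- Residual degrees of freedom go from 45 − 4 = 41 to 40.

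**The case against.** The strongest reply is that no site effect is documented. The outcomes are within-subject changes, so a constant offset between laboratories cancels, and only a site difference in change matters. Both laboratories share supervision and have worked in parallel, every visit follows one format, and the task adapts to hold performance near 70% correct. Even the drift shift of about 0.12 is small beside a standard error of 0.44. All of this stands, and it limits the size of the point. It does not remove it: sampling error is shown by the planned confidence intervals, whereas a shift from site mix is not.

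Three stronger readings are tempting, and the documents do not support them.

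- **That placebo is allocated without regard to site.** This would be an inference from silence. The schedule may be per site. The protocol refers to the main grant for further detail, and the SAP text available stops within Aim 1. What can be said is that site is not named as a factor.
- **That a site will often lack a placebo comparator.** Under site-blind allocation, the chance that all 3 placebo subjects of a cohort are at one site is [C(a,3) + C(15 − a,3)]/C(15,3): 91/455 = 20% at 8:7 and 221/455 = 49% at 12:3. But the planned contrast uses the pooled 9. There, the chance that a site has none is (56/455)³ + (35/455)³ = 0.2% at 8:7 and (220/455)³ + (1/455)³ = 11% at 12:3. The per-cohort figures matter only if the placebo groups are kept separate.
- **That site stands for inpatient versus outpatient care.** The Emergencies section says that procedures of the "inpatient unit NKI, and the Lieber Clinic will be followed". That lists whose emergency procedures apply; it does not say which patients each site enrols.

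**Conclusion.** The point holds as a gap in the analysis: the between-group d takes no account of site, although dose, cohort and calendar order coincide and the comparator is pooled across cohorts. With a steady site mix, the result is chance imbalance with mean zero, about 0.10 in d at 8:7. With a drifting mix it is systematic, about 0.11 to 0.12 at the outer doses in the example. Taking moderate as d = 0.5, a convention that the protocol does not state, that is between a fifth and a quarter of the threshold. All of these sizes rest on the assumed 0.5 SD site difference and the assumed splits. If change scores do not differ by site, the bias is zero. The within-group d values do not use placebo and are outside this point.

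**What to change.** In the SAP's Aim 1 Analysis, estimate each dose-minus-placebo mean change from a linear model with treatment group (three doses and pooled placebo) and site as terms. Divide by the SD that the SAP already names, so that the adjusted and unadjusted d differ only in the numerator, and report both. Apply the placebo-pooling check after allowing for site, for example by comparing the three placebo means from a model with the six cohort-by-arm groups plus site.

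The cost is one degree of freedom in a small sample and, in the drift example, about 1.5% on the standard error; no new data are needed. The term removes an additive site difference only. It does not address a treatment effect that varies by site, or other changes over time between cohorts.

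A cap of at most 2 of the 3 placebo places at either site may look like a natural remedy, but it should not be adopted. It leaves drift in place and makes the allocation ratio differ by site. At 12:3, with the permitted schedules equally likely, 198 have two placebo subjects at the larger site and 36 have one. The mean is (2 × 198 + 36)/234 = 1.846, so the larger site's share is 1.846/3 = 0.615 of placebo against (12 − 1.846)/12 = 0.846 of active.

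If the schedule for cohorts not yet started is being revised anyway, spreading placebo places over the sites in proportion to enrolment is optional, and only together with the site term. One sentence stating whether the list is common or per site would settle the allocation question.
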